8.2.1 Individual Discontinuation Criteria

- A participant may withdraw completely from the study at any time at his/her own request, or may be withdrawn at any time at the discretion of the investigator for safety, behavioral, compliance, or administrative reasons. The participant will be permanently discontinued both from the study intervention and from the study at that time. This is expected to be uncommon. Stopping study intervention is not considered withdrawal from the study.
- At the time of discontinuing from the study, if possible, an early termination visit should be conducted, as shown in the Schedule of Activities. See the Schedule of Activities for data to be collected at the time of study discontinuation and follow-up and for any further evaluations that need to be completed.

8.3 Lost to Follow-up

- All reasonable efforts must be made to locate participants to determine and report their ongoing status. This includes follow-up with persons authorized by the participant.
- Lost to follow-up is defined by the inability to reach the participant after a minimum of 3 documented phone calls, faxes, or emails as well as lack of response by participant to one registered mail letter. All attempts should be documented in the participant's medical records.
- If it is determined that the participant has died, the site will use permissible local methods to obtain date and cause of death.
- If investigator's use of third-party representative to assist in the follow-up portion of the study has been included in the participant's informed consent, then the investigator may use a Sponsor-retained third-party representative to assist site staff with obtaining participant's contact information or other public vital status data necessary to complete the follow-up portion of the study.
- The site staff and representative will consult publicly available sources, such as public health registries and databases, in order to obtain updated contact information.
- If after all attempts, the participant remains lost to follow-up, then the last known alive date as determined by the investigator should be reported and documented in the participant's medical records.

9 STUDY ASSESSMENTS AND PROCEDURES

Study procedures and timing are summarized in the Schedule of Activities (see Section 2).

Protocol waivers or exemptions are not allowed.

All immediate safety concerns must be discussed with the Sponsor immediately upon occurrence or awareness to determine if the participant should continue or discontinue treatment.

Adherence to the study design requirements, including those specified in the Schedule of Activities, is essential and required for study conduct.

All screening evaluations must be completed and reviewed to confirm that potential participants meet all eligibility criteria before randomization. The investigator will maintain a screening log to

record details of all participants screened and to confirm eligibility or record reasons for screening failure, as applicable.

Procedures conducted as part of the participant's routine clinical management (eg, blood count) and obtained before signing of the ICF may be utilized for screening or baseline purposes provided the procedure meets the protocol-defined criteria and has been performed within the timeframe defined in the Schedule of Activities.

Additional measures, including non-study required laboratory tests, should be performed as clinically indicated or in compliance with local regulations. Laboratory toxicities (eg, suspected drug-induced liver enzyme evaluations) will be monitored during the follow-up phase via on-site/local laboratories until all study treatment-related toxicities resolve, return to baseline, or are deemed irreversible.

If a participant shows pulmonary-related signs (eg, hypoxia, fever, or cough) or symptoms (eg, dyspnea) consistent with possible pulmonary AEs, the participant should be immediately evaluated to rule out pulmonary toxicity, according to the suspected pulmonary toxicity management algorithm in Appendix 9.

Some of the assessments referred to in this section may not be captured as data in the CRF. They are intended to be used for safety monitoring by the treating physician. Additional testing or assessments may be performed as clinically necessary or where required by institutional or local regulations.

9.1 Efficacy Assessments

Efficacy assessments for the anti-tumor activity of BMS-986249, alone and in combination with nivolumab, ipilimumab in combination with nivolumab, and nivolumab monotherapy will be based on tumor measurements, using RECIST v1.1 (all indications except prostate) or PCWG3 criteria (for prostate cancer).

Only data for the procedures and assessments specified in this protocol should be submitted to the Sponsor or Designee on a CRF. Additional procedures and assessments may be performed as part of standard of care. However, data for these assessments should remain in the participant's medical record and should not be provided to the Sponsor or Designee, unless specifically requested from BMS or Designee.

9.1.1 Imaging Assessment for the Study

Images will be submitted to an imaging core laboratory and, at the Sponsor's discretion, may be reviewed by BICR at a later date or at any time during the study. Sites should be trained prior to scanning the first study participant. Image acquisition guidelines and the submission process will be outlined in the CA030001 Imaging Manual to be provided by the core laboratory.

Screening, on-treatment, and follow-up images should be acquired as outlined in Section 2. Tumor assessments at other time points may be performed if clinically indicated and should be submitted to the central imaging vendor.

Contrast-enhanced CT of the chest, abdomen, pelvis, and all other known/suspected sites of disease should be performed for tumor assessments.

Protocol Amendment No.: 09

For participants with HCC, a triphasic CT/MRI of the liver is required.

For participants with TNBC without measurable lesions outside of the breast, contrast-enhanced MRI of the breasts should be performed along with body imaging.

Participants with prostate cancer should have bone lesions assessed using technetium-99m radionuclide bone scans at each imaging assessment. Anterior and posterior whole body planar images should be acquired. Additional (including spot views and single-photon emission computerized tomography) images should also be submitted if acquired. Participants with other malignancies may have bone scans as clinically indicated.

Images should be acquired with slice thickness of 5 mm or less with no intervening gap (contiguous). Every attempt should be made to image each participant using an identical acquisition protocol on the same scanner for all imaging time points. Tumor measurements should be made by the same investigator or radiologist for each assessment whenever possible.

Should a participant have contraindication for a CT IV contrast, a non-contrast CT of the chest and a contrast-enhanced MRI of the abdomen, pelvis, and other known/suspected sites of disease should be obtained. If the primary tumor is not of lung origin, a contrast-enhanced MRI of the chest may be obtained instead of a non-contrast CT of the chest.

Should a participant have contraindication for both MRI and CT IV contrasts, a non-contrast CT of the chest and a non-contrast MRI of the abdomen, pelvis, and other known/suspected sites of disease should be obtained. If the primary tumor is not of lung origin, a non-contrast MRI of the chest, abdomen, pelvis, and other known/suspected sites of disease is also acceptable.

Should a participant have contraindication for MRI (eg, incompatible pacemaker) in addition to contraindication to CT IV contrast, a non-contrast CT of the chest, abdomen, pelvis, and other known/suspected sites of disease is acceptable.

Use of CT component of a positron emission tomography (PET)/CT scanner: Combined modality scanning such as with PET-CT is increasingly used in clinical care and is a modality/technology that is in rapid evolution; therefore, the recommendations outlined here may change rather quickly with time. At present, low-dose or attenuation correction CT portions of a combined PET-CT are of limited use in anatomically based efficacy assessments; therefore, it is suggested that they should not be substituted for dedicated diagnostic contrast-enhanced CT scans for anatomically based RECIST measurements. However, if a site can document that the CT performed as part of a PET-CT is of identical diagnostic quality to a diagnostic CT (with IV and oral contrast), then the CT portion of the PET-CT can be used for RECIST v1.1 measurements. Note, however, that the PET portion of the CT introduces additional data that may bias an investigator if it is not routinely or serially performed.

Bone scan or PET scan is not adequate for assessment of RECIST v1.1 response in target lesions. In selected circumstances where such modalities are the sole modality used to assess certain non-target organs, those non-target organs may be evaluated less frequently. For example, bone scans may need to be repeated only when CR is identified in target disease or when progression in bone is suspected.

Brain and/or bone scans may be collected per local standards, as clinically indicated.

Tumor assessments for all participants should continue per protocol even if dosing is delayed or discontinued. Changes in tumor measurements and tumor responses will be assessed by the investigator per study design using RECIST v1.1 or PCWG3 (for prostate cancer) criteria.

Assessments of PR and CR must be confirmed at least 4 weeks after initial response. A Best Response of SD can only be made after the participant is on-study for a minimum of 49 days from the date of treatment initiation (ie, first dose). Investigators will also report the number and size of new lesions that appear while on study. Investigators will also report the number and size of new lesions that appear while on study treatment. The time point of tumor assessments will be reported on the CRF based on the investigator's assessment.

9.2 Adverse Events

The definitions of an AE or SAE can be found in Appendix 3.

AEs will be reported by the participant (or, when appropriate, by a caregiver, surrogate, or the participant's legally authorized representative).

The Investigator and any Designees are responsible for detecting, documenting, and reporting events that meet the definition of an AE or SAE and remain responsible for following up AEs that are serious, considered related to the study treatment or the study, or that caused the participant to discontinue before completing the study.

Contacts for SAE reporting specified in Appendix 3.

9.2.1 Time Period and Frequency for Collecting AE and SAE Information

For all study participants, safety reporting of all AEs (non SAEs and SAEs) should take place from date of informed consent through 100 days post EOT. All SAEs, and all AEs (SAEs and non-serious AEs) associated with confirmed or suspected SARS-CoV-2 infection, must be collected from the date of the participant's written consent through 100 days following EOT.

The IB describes the Reference Safety Information to determine expectedness of SAEs for expedited reporting. Following the participant's written consent to participate in the study, all SAEs, whether related or not related to study treatment, must be collected, including those thought to be associated with protocol-specified procedures.

- All AEs and SAEs must be collected that occur during the screening period and through 100 days post EOT, except in cases where a study participant has started a new anti-neoplastic therapy. Any SAE occurring after the start of a new anti-neoplastic therapy that is suspected to be related to study treatment by the investigator should be reported as an SAE.
- The investigator must report any SAE that occurs after these time periods and that is believed to be related to study treatment or protocol-specified procedure.
- Medical occurrences that begin before the start of study treatment but after obtaining informed consent will be recorded on the appropriate section of the CRF section.
- All SAEs will be recorded and reported to Sponsor or designee within 24 hours, as indicated in Appendix 3.

• The investigator will submit any updated SAE data to the Sponsor within 24 hours of this being available.

Investigators are not obligated to actively seek AEs or SAEs in former study participants. However, if the investigator learns of any SAE, including a death, at any time after a participant has been discharged from the study, and he/she considers the event reasonably related to the study treatment or study participation, the investigator must promptly notify the Sponsor.

The method of evaluating and assessing causality of AEs and SAEs and the procedures for completing and reporting/transmitting SAE reports are provided in Appendix 3.

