Viral Markers	X	Х	X			For participants with HCC only. To be completed at central laboratory. For HCV-infected; HCV RNA. For HBV-infected; HBV DNA. See Section 9.4.4 and Table 9.4.4-1.	
PSA	progression or the	start of subsequ	ient systemic ca	ncer therapy, whichever of	ccurs later. PSA evaluation	n follow-up until radiographic on beyond radiographic ression should be performed as	
Adverse Event Repor	ting and Concomita	ant Medication	Assessments				
Monitor for Non-SAEs ^b	X	X	X			For all study participants, safety reporting of AEs and SAEs should take place from date of informed consent through 100 days post EOT.	
Monitor for SAEs ^b	X	X	X			For all study participants, safety reporting of AEs and SAEs should take place from date of informed consent through 100 days post EOT.	
Concomitant Medication Assessments	X	X	Х			Including antiviral therapy for HCC participants.	

Table 2-5: Follow-up Procedural Outline for All Study Parts

	Sa	fety Follow-up								
Procedure	Follow-up 1 30 Days ^a (± 7 Days)	Follow-up 2 60 Days ^a (± 7 Days)	Follow-up 3 100 Days ^a (± 7 Days)	ays ^a Imaging Follow-up Survival Follow		Notes				
Sample Collection						See Section 9.5, and Table 9.5-2 through Table 9.5-9 for the sample collection schedule.				
Efficacy Assessments										
Tumor/Response Assessments	Part 1: Tumor assessments should occur Q12W (± 7 days), starting from the date of the last on-treatment tumor assessment. Part 2A: The first tumor imaging assessment should occur 12 weeks (± 7 days) from first dose. Subsequent tumor imaging assessments should occur Q8W (±7 days) from the date of the first tumor imaging assessment until Week 52 then continue Q12W (±7 days) thereafter. For Part 2B: Tumor imaging assessments should occur Q8W starting from the first dose (±7 days) up until Week 48, and then continue Q12W (± 7 days). For participants with HCC, a triphasic CT/MRI of the liver is required. For participants with TNBC without measurable lesions outside of the breast, contrast-enhanced MRI of the breasts should be performed along with body imaging. For all study parts: The duration of the Imaging Follow-up Period will be 100 days post EOT, or until initiation of another anti-cancer treatment, or death, whichever occurs first. See Section 9.1.1.									
Brain Imaging				ld have surveillance MRI p ast can be performed if MR		Q12W or sooner if clinically Section 9.1.1.				

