Variable: Treatment Related AE with CTCAE Grade 3 or higher that occurred within 24 weeks from first dose Intercurrent events: early discontinuation of study

Treatment Policy: Patients that discontinue treatment early will have a 100 days post last dose safety follow-up. AEs occurring after this safety follow-up window will not be included in the analysis, even if they occurred within the 24 weeks from first dose.

Intercurrent event: initiation of subsequent anti-cancer therapy

While on treatment: Patients that initiate an anti-cancer subsequent therapy will be discontinued from study but will be followed up for safety events 100 days from last dose. Safety events regardless of whether they occur before or after subsequent therapy will be include in the analysis. AEs occurring past 100 days safety follow-up will not be included in the analysis, even if they occurred within the 24 weeks from first dose.

Intercurrent event: death and withdrew

While on treatment: Patients who die or withdraw consent before reaching the 24 weeks landmark will be included in the analysis and their Grade 3 to 5 treatment related AEs will be include in the summary.

Population level summary: Grade 3 to 5 treatment related adverse event incidence rate, comparison of Arm C vs Arm D and Arm F vs Arm D with estimated difference and odd ratio and 80% confidence interval using Cochran Mantel Haenszel methodology adjusting for stratification factors will be computed. Adjusted and unadjusted chi square test will be performed and p-values will be provided.

Objective	Endpoint
Primary	Primary
To evaluate the preliminary efficacy of BMS-986249 in combination with nivolumab (Arm C and Arm F) relative to historic nivolumab monotherapy data in participants with previously untreated, unresectable or metastatic melanoma	ORR as assessed by investigator using RECIST v1.1

Main Estimand for the Primary Objective

Treatment: 1200 mg BMS-986249 IV Q8W + 480 mg nivolumab IV Q4W (Arm C); 3 mg/kg ipilimumab Q3W + 1 mg/kg nivolumab IV Q3W for 4 doses followed three weeks later by 480 mg nivolumab IV Q4W(Arm D); 600 mg BMS-986249 IV Q4W + 480 mg nivolumab IV Q4W (Arm F)

Population: All treated participants with evaluable baseline tumor assessment per RECIST v1.1

Variable: BOR, defined as the best response, as determined by investigator, per RECIST 1.1

Intercurrent events: early discontinuation of study

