5.1.5 Follow-up

5.1.5.1 Safety Follow-up Period

Upon completion of study therapy (or up to a maximum of 2 years, if applicable) or once the decision is made to discontinue the participant from treatment, that is, at end of treatment (EOT), all participants will enter a Safety Follow-up Period.

For participants who will complete all scheduled cycles of therapy, the EOT visit will be the same visit as the last scheduled and completed on-treatment visit and will be the start of the Safety Follow-up Period. For participants who will not complete all scheduled cycles of therapy, the EOT visit will be the most recent on-treatment visit (with all available safety and response data) and will not need to be repeated. Accordingly, for these participants, this visit will be considered the start of the Safety Follow-up Period.

After the EOT visit, follow-up study visits should occur at Days 30, 60, and 100 (±7 days) for all study participants. Safety reporting of AEs and SAEs should take place from date of informed consent through 100 days post EOT.

All participants should complete the 3 clinical safety follow-up visits regardless of whether new anti-cancer therapy is started, except those participants who withdraw consent for study participation.

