The final analysis will take place when all randomized participants have completed at least 36 weeks follow-up or discontinue earlier. Due to exploratory nature of the proof of concept (PoC) design, no multiplicity adjustment will be made for testing multiple endpoints or multiple treatment arms.

10.1.2.2 Changes to Sample Size Assumptions for Revised Protocol 07

[figure not shown]
The original sample size calculation was based on a 60% two-sided CI of ORR for the difference between treatments and required 54 participants per arm. As participants in Arm E will not be randomized as originally planned, the efficacy evaluation and the statistical comparison will use a reference value of based on nivolumab monotherapy historical data in melanoma (see Section 5.4.7.2).

One of the main objectives of this study is to evaluate the preliminary safety and tolerability of BMS-986249 in combination with nivolumab (Part 2A Arm C and Arm F).

Based on final analysis of CA209511, the ipilimimab 3 mg/kg in combination with nivolumab 1 mg/kg, the incidence rate of drug-related Grade 3-5 AEs within 24 weeks is estimated to be relative improvement in the incidence of Grade 3-5 TRAEs is considered to be clinically relevant.

Using a two group $\chi 2$ test with a 0.10 one-sided significance alpha level, assuming a 1:1 randomization ratio of experimental BMS-986249 in combination with nivolumab containing regimen to control ipilimumab in combination with nivolumab, a sample size of 60 participants per arm will have approximately 70% power to detect a ratio in favor of the alternative hypothesis of compared to the null hypothesis proportion of

The null hypothesis is the ratio of proportions above or equal to 1, the alternative hypothesis is the ratio of proportion is below to 1.

Protocol Amendment No.: 09 Date: 14-Mar-2023

e: 14-Mar-2023

The final analysis will take place when all randomized participants have completed at least 36 weeks follow-up or discontinue earlier. Due to exploratory nature of the PoC design, no multiplicity adjustment will be made for testing multiple endpoints or multiple treatment arms.

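### One bullet in Section 9.2.1 exempts adverse events after new anti-cancer therapy, against the rest of the protocol and both primary safety estimands

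*Combined protocol and SAP*

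**What the plan says.** Section 9.2.1 states two rules. Its opening sentence applies to all participants: "safety reporting of all AEs (non SAEs and SAEs) should take place from date of informed consent through 100 days post EOT". Its first bullet makes collection mandatory "through 100 days post EOT, except in cases where a study participant has started a new anti-neoplastic therapy". For the time after new therapy the bullet restores one category only: "Any SAE occurring after the start of a new anti-neoplastic therapy that is suspected to be related to study treatment by the investigator".

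Other parts of the protocol repeat the unrestricted rule. Table 2-5 (follow-up procedures) has "safety reporting of AEs and SAEs should take place from date of informed consent through 100 days post EOT", and Section 9.4 says the same. Section 5.1.5.1 adds: "All participants should complete the 3 clinical safety follow-up visits regardless of whether new anti-cancer therapy is started"; it exempts only participants who withdraw consent.

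The primary safety endpoint in Parts 2A and 2B is the incidence of treatment-related Grade 3-5 AEs within 24 weeks of first dose, among all treated participants. For subsequent anti-cancer therapy, Tables 4-4 and 4-5 state: "Safety events regardless of whether they occur before or after subsequent therapy will be include in the analysis". Events later than 100 days after the last dose are left out. The paragraph that carries this rule opens "While on treatment: Patients that initiate an anti-cancer subsequent therapy will be discontinued from study".

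**The concern.** The estimand can count only what the sites record. Sections 9.2.1 and 5.1.5.1, Table 2-5 and Section 9.4 tell sites to keep collecting after new therapy; one bullet in 9.2.1 tells them not to, except for related serious adverse events (SAEs). The opening sentence of 9.2.1 is worded as a recommendation and the bullet as an obligation with an exception, so a site could reasonably take the bullet as the operative rule.

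The endpoint variable has no seriousness requirement. The denominator is all treated participants, and no imputation or censoring is described for events that were not collected. An uncollected event therefore becomes a non-event.

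This is a primary endpoint in both parts, and the sample sizes rest on it: in Section 10.1.2.2, "a sample size of 60 participants per arm will have approximately 70% power" for the Part 2A comparison, and in Section 10.1.3, 40 per cohort for about 95% power in Part 2B. Each Part 2B cohort is tested against a fixed null proportion, so a lost event can only make the result look safer. In Part 2A a loss in Arm D lowers the control rate and works against BMS-986249, while a loss in Arm C or Arm F favours it.

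A smaller, separate point is that the safety estimands label the subsequent-therapy strategy as while-on-treatment, although their text keeps events after new therapy. The label contradicts the rule beneath it.

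**Working it through.** **Step 1. The rules side by side, for a non-serious related Grade 3-4 event after new therapy, inside 24 weeks and inside 100 days of last dose.**

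| Place | Collected or counted? |
|---|---|
| 9.2.1, opening sentence | Collected |
| 9.2.1, first bullet | Exempt; only related SAEs restored |
| Table 2-5; Section 9.4 | Collected |
| Section 5.1.5.1 | Collected; all three visits held despite new therapy |
| Tables 4-4 and 4-5 (safety) | Counted |

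The first bullet is the only entry that differs.

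**Step 2. What must happen for an event to be lost.** All of these are needed:

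- the participant stops study treatment and starts new therapy before Week 24;
- the related Grade 3-4 event begins after that start, within 24 weeks of first dose and 100 days of last dose;
- it is non-serious (Grade 5 events are serious by definition, so they are kept);
- the participant has no other qualifying event;
- the site follows the bullet and not the general rule.

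**Step 3. Unit effect.** With n participants in the arm or cohort, one such participant lowers the observed rate by 1/n.

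- Part 2A arm, n = 60 (Section 10.1.2.2): 1/60 = 0.0167, or 1.7 percentage points.
- Part 2B cohort, n = 40 (Section 10.1.3): 1/40 = 0.025, or 2.5 points.

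**Step 4. Follow-up time exposed (illustration).** Assume new therapy starts on the day the next dose was due. Days removed = 100 − dosing interval.

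- 4-week cycles: 100 − 28 = 72 of 100 days.
- Arm D combination phase, 3-week cycles: 100 − 21 = 79 of 100 days.

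These days matter only up to 24 × 7 = Day 168. Window end = day of last dose + 100.

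- 4-week cycles, last dose on Day 1, 29 or 57: Day 101, 129 or 157.
- Arm D, last combination dose on Day 1, 22, 43 or 64: Day 101, 122, 143 or 164.

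In all these cases the whole window lies inside the 24-week period.

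**Step 5. The stated power.** The Part 2A figure of about 70% cannot be reproduced, because the control rate and target ratio are blacked out. On assumed values, the two-proportion formula with pooled null variance is

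power = Φ{[(p0 − p1) − z(0.90)·√(2p̄(1 − p̄)/n)] / √([p0(1 − p0) + p1(1 − p1)]/n)}.

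With n = 60, p0 = 0.45 and p1 = 0.291: p̄ = 0.3705; (0.159 − 1.2816 × 0.0882)/0.0870 = 0.53; power = 0.70. Over assumed control rates of 0.30 to 0.60, the experimental rate giving 70% power runs from 0.162 to 0.436.

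Suppose 10% of participants with an event were missed. The documents do not support this or any other share; it serves only to show direction.

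| Where missed | Result |
|---|---|
| Both arms equally | Power 0.64-0.66; ratio unchanged |
| Control arm only | Power 0.44-0.57 |
| Experimental arm only | Apparent power 0.78-0.85 |
| Experimental arm only, true rates equal (control 0.30-0.55) | One-sided rejection rate 0.18-0.25 instead of 0.10 |

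**The case against.** The strongest reply is that the practical loss is probably small.

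- The unrestricted rule appears in all the main schedules as well as in Sections 5.1.5.1 and 9.4, so a site would have to follow one bullet against many other statements.
- Section 9.2.3 requires every identified non-serious AE to be recorded, and Section 9.4.4 requires clinically significant laboratory abnormalities to go on the AE page.
- Many related Grade 3-4 events are reportable as SAEs in any case: important medical events (Appendix 3), Grade 3-4 infusion reactions (Section 7.5.5) and potential drug-induced liver injury (Section 9.2.8).
- Many participants who stop for related toxicity already have a qualifying event, because events meeting the dose-limiting toxicity criteria lead to discontinuation (Sections 7.5.1 and 8.1).
- Section 5.5.1.3 reports that most immune-related events on ipilimumab 3 mg/kg arise within 12 weeks, with a median onset of 4.6 weeks for Grade 2-4. The first Part 2A scan is at 12 weeks, so a switch prompted by a scan would usually follow that peak.

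These points narrow the exposed set, and they are why no total loss is claimed here. They do not remove the exception. Section 9.2.3 gives no collection period. The onset data concern ipilimumab, not BMS-986249, and Part 2B scans begin at Week 8.

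It is also fair to say that the 72 and 79 days measure calendar time and not event risk, and that their assumption about when new therapy starts has no support in the documents; they are illustrations only. The label is a matter of naming: the text beneath it already says what is counted.

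**Conclusion.** The concern holds. The first bullet of Section 9.2.1 contradicts its own opening sentence, Table 2-5, Sections 5.1.5.1 and 9.4, and the primary safety estimands of Parts 2A and 2B. This is certain from the text.

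The effect on the endpoint is possible but cannot be sized. It is limited to non-serious related Grade 3-4 events that begin after new therapy, in participants with no other qualifying event, at sites that follow the bullet. Per participant it is 1.7 percentage points in a Part 2A arm of 60 and 2.5 points in a Part 2B cohort of 40. It can only understate incidence in Part 2B. In Part 2A the documents do not show which arm would lose more.

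It should be fixed, because the endpoint is primary, the wording is wrong as it stands, and events not collected at the time may be hard to recover.

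**What to change.** In the first bullet of Section 9.2.1, delete the exception, that is, everything from the word except to the end of that sentence. All AEs are then collected to 100 days after EOT whether or not new therapy has started, as the protocol already says elsewhere. The following sentence on related SAEs becomes redundant but no longer conflicts.

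In the safety estimands of Tables 4-4 and 4-5, relabel the subsequent-therapy strategy from while-on-treatment to treatment policy within the 100-day safety window, so that it matches its text. Leave unchanged the early-discontinuation label, the objective response estimand and the planned analysis of proportions (Cochran-Mantel-Haenszel and chi-square).

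The cost is one deleted clause and one corrected label in two tables. The Day 30, 60 and 100 visits are already required regardless of new therapy. Sites will have some additional AEs to enter and attribute after new therapy, and the reported rate may come out slightly higher.
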